8.2 STATISTICAL ANALYSIS PLANS

We will summarize baseline variables and covariate data using standard descriptive statistics (frequencies and proportions for categorical variables; means, standard deviations, quartiles, the minimum and maximum for continuous variables). This will allow us to identify baseline imbalances that are due to random chance and possible missing data.

The primary analysis is a comparison of mean NRS pain scores between the two treatment groups at the second postoperative day. This analysis will be conducted with a linear regression model that includes an indicator variable for the usual care without ACC group (the test on the coefficient, denoted β_1 , of which will form the primary comparison of interest), and covariates identified as poorly balanced at baseline (i.e., a 20% between-group difference, in general). Note that β_1 represents the difference in mean NRS pain score at the second postoperative day between the usual care without ACC group and use of ACC group, holding all other covariates fixed. The null hypothesis for the test of noninferiority assumes that the usual care without ACC is inferior to the use of ACC (specified in Section 8.1); in terms of the linear regression model, this corresponds to $H_0: \beta_1 \geq \delta$, where δ is the pre-specified noninferiority margin of 2.0. The alternative hypothesis assumes that the usual care with ACC is noninferior to the use of ACC, $H_A: \beta_1 < \delta$. Noninferiority is established at the $\alpha=0.025$ level if the upper bound of the 95% confidence interval lies below the noninferiority margin, $\delta = 2.0$. The primary analyses will be conducted under the principle of intention-to-treat, which is, admittedly, controversial as some authorities assert that intention-to-treat is non-conservative in the setting of a noninferiority trial (36); missing data will be imputed using a standard multiple-imputation algorithm. As a secondary analysis, we will also repeat the primary analyses under a per-protocol paradigm. Finally, since the NRS is a fundamentally ordinal scale, we will verify the bivariate comparison with a non-parametric Wilcoxon rank-sum test that requires no distributional or linear-scale assumptions. All analyses will be conducted with updated versions of the SAS (37) and Stata (19) statistical packages.

For our secondary aims, we will use the following analytic approaches:

Secondary Aim 1: The first secondary analysis is a comparison of the mean NRS pain scores between the two treatment groups over the two-week follow-up period. We will have up to 15 measurements per individual (daily pain scores over a two-week period including baseline measurement). We are primarily interested in whether the rate of change in NRS pain score over the two-week follow-up period differs between the two treatment groups. These analyses will be conducted with linear mixed-effects models (38,39) that include terms for the effects of time, study group and the group-by-time interaction which will serve as the primary statistical test of the study hypothesis. Subjects will be included as random effects, and the within-subject correlation will be modeled appropriately. The most appropriate error structure will be chosen by comparing model fit using Akaike's Information Criterion (40). The overall difference between two total response curves will be tested with likelihood-ratio tests. The predicted

(modeled) change in the outcome over the relevant follow-up period will be obtained from each model along with the associated standard errors from which 95% confidence intervals will be constructed.

Secondary Aim 2: The mean difference in two-week postoperative opioid use (measured in total morphine equivalents) between the two treatment groups will be compared with a two-sample t-test. A secondary analysis will be conducted with a multiple linear regression model with an indicator variable for treatment group (for which the test of $\beta_1=0$ will form the primary hypothesis test) and adjustment for baseline covariates, use of opioids at baseline, and baseline NRS pain score.

Secondary Aim 3: The frequencies of complications related to ACC will be summarized with proportions and associated exact 95% confidence intervals.

Secondary Aim 4: To identify candidate predictors of differential response to the ACC, we will consider including interaction terms between the treatment indicator and demographic variables and baseline pain NRS scores in the primary linear regression analysis.

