1.3 STUDY DESIGN

This is a randomized, open-label, two-arm, parallel-comparison noninferiority clinical trial of usual care with an ACC placed preoperatively compared to usual care without an ACC among adult patients undergoing elective unilateral TKA at the KPNC San Leandro Medical Center (Figure).

All patients meeting eligibility criteria will be introduced to the study by the treating orthopedist and PI, [name], at the patient's first clinic visit. If the patient expresses interest in study participation, they will be consented over the phone by the clinic Physician's Assistant (PA). Baseline data will be obtained via a telephone call with the study Research Assistant 7-10 days prior to the date of surgery. Randomization will occur in the preoperative area immediately prior to surgery. Patients will keep a daily diary of their pain levels and analgesic medication use for two weeks postoperatively and will be called by the study Research Assistant on post-op day two and day 14. A single electronic

medical record (EMR) data extraction for adverse events (focusing on emergency department and inpatient visits) will be conducted at 30 days postoperatively.

The primary outcome is the absolute pain score on post-op day two, measured on an 11-point numerical rating scale; the noninferiority margin for this comparison is set *a priori* at 2.0 points. Secondary outcomes include the total amount of opioid consumed over the two-week post-op period, the overall pain scores over the two-week post-op period, and adverse events directly attributed to the ACC.

[figure not shown]

Figure: Study Design Schema

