3.2 EXCLUSION CRITERIA

The exclusion criteria for the ACCESS study, and their rationales, are:

1. Patient declines use of ACC	1. Patient not eligible for ACC study arm
2. Surgeon decides that an ACC will not be placed for any reason	2. Patient not eligible for ACC study arm
3. Known hypersensitivity to ropivacaine or any alternative anesthetic for ACC use	3. Patient not eligible for ACC study arm
4. Hypersensitivity or inability to tolerate peri-articular injections of clonidine, epinephrine, bupivacaine and ketorolac	4. Participants in both arms of the trial are required to undergo peri-articular anesthetic injections
5. Any evidence of substance-use disorder in past year	5. Opioid use is a secondary study outcome measure
6. Non-English speaking	6. Study instruments are all in English
7. Failure to complete all baseline study instruments prior to surgery	7. No baseline measurement available for calculating change
8. Requires secondary procedure at time of TKA (e.g., removal of hardware)	8. Complex surgery may cause change in outcome measures independent of study objectives
9. Not intending to use spinal anesthesia for TKA procedure	9. Atypical surgical approach
10. Actively enrolled in KPNC chronic-pain program	10. Opioid use is a secondary study outcome measure
11. Having been prescribed long-acting opioid (e.g., Oxycontin, MS Contin) within 90 days prior to enrollment	11. Pre-surgery major opioid use may complicate measurement of post-surgery opioid use
12. Inability to tolerate any oral NSAID or acetaminophen or any short-acting opioid	12. NSAIDs, acetaminophen, and short-acting opioids are used for analgesia for all participants

These exclusion criteria are established for safety and to ensure consistency in the participant sample.

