6.3 PREOP TELEPHONE CALL

Approximately one-week prior to the participants TKA surgery, the study Research Assistant will call the patient at home to ensure that they are still intending to follow through with all study procedures and to ensure they understand the details of their further participation, including the randomization immediately prior to surgery. If the patient has any questions, they will be referred to the DOR co-PI ([name]) for further discussions. If the patient expresses any reservations about their further involvement in the study, they will not be randomized. If the patient is fully intending to continue with the study, the RA will administer the baseline questionnaire over the phone before ending the call.

During this call, the RA will also conduct a repeat eligibility screen to ensure that the patient meets all inclusion and none of the exclusion criteria.

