Note on the revised calculations: Blinded study data were examined twice, most recently after 98 participants were enrolled and the assumed standard deviation of 2.04 was revised upward to 2.64 based on this analysis. In addition, the survey of knee-arthroplasty specialty KPNC orthopedic surgeons conducted by the Principal Investigator showed that 84% of the 19 respondents would set the noninferiority margin at 2.0 points or more. In the original power calculations, we assumed a noninferiority margin of 1.5 points, in order to be highly conservative. However, after further reflection and sensitivity analyses, we found that adopting such a strict noninferiority margin could substantially impair our ability to declare noninferiority for an observed nonzero difference. Therefore, we reset the noninferiority margin back to 2.0 points, consistent with the responses to the orthopedist survey. Finally, in order to retain a very high likelihood of affirming noninferiority if the point estimate of the between-group difference in the outcome pain scores was less than the noninferiority margin, we decreased the beta to 0.02 (power = 0.98).

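### The primary noninferiority model picks covariates by chance baseline imbalance on an undefined 20% rule, so baseline pain enters only by luck

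*Combined protocol and SAP*

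**What the plan says.** The primary analysis in section 8.2 is a "linear regression model that includes an indicator variable for the usual care without ACC group", to which are added "covariates identified as poorly balanced at baseline (i.e., a 20% between-group difference, in general". Noninferiority is declared if the upper 95% confidence bound on the treatment coefficient (no catheter minus catheter) is below 2.0. No covariate is named for this model.

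Baseline pain is collected before randomization. Section 1.3 states: "Baseline data will be obtained via a telephone call with the study Research Assistant 7-10 days prior to the date of surgery". Section 6.3 says of that call that "the RA will administer the baseline questionnaire over the phone before ending the call". The footnote to Appendix 1 lists the NRS among the questionnaire items. Section 3.2, criterion 7, excludes patients for "Failure to complete all baseline study instruments prior to surgery". Randomization is unstratified (section 3.3).

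Elsewhere in section 8.2, the secondary regression for Secondary Aim 2 specifies "adjustment for baseline covariates, use of opioids at baseline, and baseline NRS pain score".

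**The concern.** Under randomization, baseline imbalance arises by chance and says nothing about whether a variable predicts day-2 pain. A rule driven by imbalance can admit a variable with no bearing on the outcome and leave out one that matters.

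The rule also does not determine a model. A relative difference of 20%, a gap of 20 percentage points and a standardized difference of 0.2 can each select different covariates from the same data. No candidates are listed, and the closing qualifier leaves room for judgment in an open-label trial.

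Two things are at stake: a decision model that cannot be written down before the arms are compared, and precision given up if baseline pain is prognostic. The second matters mainly when the true difference lies between 0 and the margin. Section 8.1 shows that nonzero differences were on the investigators' minds: the margin went from 1.5 to 2.0 because the stricter value "could substantially impair our ability to declare noninferiority for an observed nonzero difference".

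**Working it through.** **Inputs from section 8.1.** 60 evaluable per arm, SD 2.64, margin 2.0, one-sided alpha 0.025, power 98%.

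**Assumed, because the documents give none.** Baseline NRS mean and SD, and the correlation r between baseline and day-2 NRS.

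**The plan's own figure.** The z-test formula gives n = 2 × 2.64² × (1.960 + 2.054)² / 2.0² = 56.1, so 57 per arm against the stated 60. At 60 per arm, power at zero difference is 98.6% (z) or 98.4% (t). The stated size is slightly generous; the gap does not affect this point.

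**Chance that baseline NRS enters the model**

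- Standardized difference above 0.2: 2 × [1 − Φ(0.2 / √(2/60))] = 27.3%.
- Relative difference above 20%: 2 × [1 − Φ(0.2 × mean / (SD × √(2/60)))]. This gives 9.7% (mean 4, SD 2.64) down to 0.28% (mean 6, SD 2.2). At mean 3 it is 13.5% to 21.3% over the same SDs.

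**Precision and power if baseline NRS is always included**

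Half-width = t(0.975) × 2.64 × √(1 − r²) × √(2/60), with 118 df unadjusted and 117 df adjusted. Power is from the noncentral t.

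| Model | Half-width | Power at 0 | Power at 0.5 | Power at 1.0 |
|---|---|---|---|---|
| Unadjusted | 0.954 | 98.4% | 87.0% | 53.9% |
| r = 0.1 | 0.950 | 98.5% | 87.3% | 54.3% |
| r = 0.2 | 0.935 | 98.8% | 88.3% | 55.6% |
| r = 0.3 | 0.911 | 99.1% | 89.9% | 57.8% |
| r = 0.4 | 0.875 | 99.4% | 92.0% | 61.2% |
| r = 0.5 | 0.827 | 99.7% | 94.6% | 66.1% |

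The adjusted rows leave out the small expected cost of chance imbalance, a factor of √(1 + 1/116) = 1.0043. With it, the half-width at r = 0.1 is 0.954, no better than unadjusted; at r = 0.3 and 0.5, power at 1.0 is 57.5% and 65.8%. Break-even is r ≈ 0.09. At r = 0 the half-width is 0.959 against 0.954, a cost under 0.005 points.

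**The imbalance rule itself**

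Simulated with 10,000 trials per setting, baseline mean 5 and SD 2.4, rounded to 0–10, baseline NRS the only candidate. Power at a true difference of 1.0:

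| | r = 0.3 | r = 0.5 |
|---|---|---|
| Rule, relative 20% | 54.3% | 54.6% |
| Rule, standardized 0.2 | 55.2% | 57.2% |
| Always included | 57.5% | 65.2% |

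A separate run of 100,000 trials for the standardized rule gave 54.7% and 57.3%, against 57.5% and 65.7% always included.

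**Type I error.** At a true difference of 2.0, over r = 0, 0.3 and 0.5, the rule rejected in 1.7% to 2.7% of trials and the fixed model in 2.2% to 2.7% (Monte Carlo SE 0.16 points). There is no inflation.

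**Does the choice of model change conclusions?** In the 100,000-trial runs, adjusted and unadjusted analyses disagreed on noninferiority in about 10% (r = 0.3) and 19% (r = 0.5) of trials at a true difference of 1.0, and in about 1% at zero.

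**Other prognostic traits.** Take eight assumed binary traits jointly explaining 18% of outcome variance, with r = 0.3. Power at 1.0 is then:

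- unadjusted, 53.6%
- rule, relative, 57.6%; rule, standardized, 55.1%
- baseline NRS alone, 57.3%
- baseline NRS plus the eight traits named in advance, 63.5%

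If the traits explain nothing, these become 51.3% (relative) and 52.4% (standardized) under the rule, 57.1% for baseline NRS alone, and 54.1% with all eight named.

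**The case against.** The strongest reply is that the only demonstrable defect is unclear wording, and that mandatory adjustment is a preference.

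- **The gain rests on an undocumented r.** This stands. For r of 0.1 to 0.2 the gain at a true difference of 1.0 is at most about 2 points of power, and at zero difference it is small for any r. But the downside is under 0.005 points of half-width, so the trade is lopsided.
- **Section 8.1 speaks of an observed difference, not a true one.** Fair. In those terms, the largest observed difference that passes is 2.0 − 0.954 = 1.05 unadjusted, 1.09 at r = 0.3 and 1.17 at r = 0.5. The shift is modest, in the direction the investigators wanted.
- **With other prognostic traits, the rule can match baseline NRS alone** (57.6% against 57.3%). True for the relative reading under those invented traits. Naming such traits in advance does better still, but only if they are well chosen, which argues for a short list.
- **Secondary Aim 2 is no precedent.** Its lead analysis is an unadjusted t-test, and baseline NRS appears only in a secondary regression. Correct; it shows only that the team regards baseline pain as a sensible adjuster.
- **Availability rests on exclusion criterion 7.** Section 8.2 allows for missing data among baseline variables, and section 6.4 describes no completeness check on the day of surgery. A few values could be missing; section 8.2 already plans multiple imputation.
- **An unadjusted check exists.** The Wilcoxon test in section 8.2 is unadjusted, but it gives no confidence interval to set against 2.0.

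**Conclusion.** The concern holds. The model that decides noninferiority is not fixed in advance: it depends on an undefined 20% threshold applied to an unlisted set of covariates. Baseline pain, required of every patient before entry, has at best about a one-in-four chance of being used, unless its mean is well below the values assumed here.

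Applied mechanically, the rule keeps type I error at or slightly below its nominal level, and the plan describes no choice of model on results. The measurable loss is precision. At a true difference of 1.0 and r between 0.3 and 0.5, always including baseline NRS adds roughly 2 to 11 points of power over the rule, depending on r and on how 20% is read. That takes baseline NRS as the only candidate; with other prognostic traits the rule recovers some or all of it. At the zero difference that reproduces the stated power, the gain is about a point.

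This does not invalidate the trial. It should be corrected because the better method is plain and nearly free. Confidence in the size is medium, since baseline mean, SD and r are assumed.

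**What to change.** In section 8.2, replace the imbalance rule with a sentence to this effect: the primary model includes treatment and the baseline NRS pain score from the preoperative call, whatever the observed balance.

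Then:

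- Name any other covariates believed prognostic before the arms are compared, and keep the list short.
- Report the unadjusted difference with its 95% CI against the 2.0 margin as a sensitivity analysis.
- Keep adjustment for chance imbalance, if wanted, as a labelled sensitivity analysis with the 20% metric and candidate list defined, and state that it cannot change the noninferiority decision.

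The cost is one or two sentences and one degree of freedom. No new data are needed.

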2.2 SECONDARY OBJECTIVES

Among a sample of patients undergoing elective primary unilateral TKA who receive peri-articular anesthetic injections:

- 1) To compare the overall two-week levels of postoperative pain between those participants randomized to ACCs containing ropivacaine and those participants randomized to usual care without an ACC
- 2) To compare the use of opioid medications (in mean total morphine milligram equivalents) between those participants randomized to ACCs containing ropivacaine and those participants randomized to usual care without an ACC over the two-week postoperative period
- 3) To estimate the incidence of complications related to ACC placement including infection, displacement, ACC-related outpatient clinic or ED visits
- 4) To conduct exploratory analyses to identify candidate predictors of differential response to the ACC; potential interacting variables for these analyses will include demographics, baseline pain NRS scores, clinical comorbidities and secondary outcome measures.

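### Secondary Aim 1: the objective asks for the mean two-week pain level, but the designated test and the only planned interval concern change over time, and no mean-difference contrast is defined

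*Combined protocol and SAP*

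**What the plan says.** Three places describe a level of pain:

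- Section 2.2, Secondary Objective 1 (also in the synopsis): "To compare the overall two-week levels of postoperative pain between those participants randomized to ACCs containing ropivacaine" and those randomized to usual care without a catheter.
- Section 1.3, among the secondary outcomes: "the overall pain scores over the two-week post-op period".
- Section 8.2, where the Aim 1 paragraph opens: "The first secondary analysis is a comparison of the mean NRS pain scores between the two treatment groups over the two-week follow-up period".

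The same Aim 1 paragraph then turns to change: "We are primarily interested in whether the rate of change in NRS pain score over the two-week follow-up period differs" between groups. It specifies a linear mixed model with time, study group and their interaction, and designates "the group-by-time interaction which will serve as the primary statistical test of the study hypothesis". It adds a second test: "The overall difference between two total response curves will be tested with likelihood-ratio tests". The only estimate given a 95% interval is the predicted "change in the outcome over the relevant follow-up period will be obtained from each model".

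The data are up to 15 measurements per person, described as "daily pain scores over a two-week period including baseline measurement". Section 1.3 puts baseline collection 7-10 days before surgery. The paragraph does not say whether time is linear or categorical, when the follow-up period starts, or where baseline sits on the time axis.

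**The concern.** A difference in mean level and a difference in rate of change are different quantities. If one arm is worse by the same amount on every postoperative day, the arms differ in level while their postoperative slopes are identical. If an early benefit fades, the slope difference can point the opposite way from the mean difference.

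An analyst who follows Section 8.2 faithfully could report a slope, a change from baseline to day 14, or a change from day 1 to day 14. In general none of these is the quantity in Objective 1. The study-group coefficient does not fill the gap: with an interaction in the model, it is the arm difference at the time origin or reference day. A null or reversed interaction could then be read as the answer on overall two-week pain, or the contrast could be settled after the data are seen in an open-label trial.

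**Working it through.** The plan states no power, effect size or SD for Aim 1, so there is no figure to reproduce. The following is an illustration.

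**Inputs from the documents.** 60 evaluable participants per arm and SD 2.64 (Section 8.1; this is the day-2 SD, applied here to all days as an assumption). Baseline plus 14 daily scores (Section 8.2). Infusion over 48-72 hours (Section 5.1, Study Device), which makes an effect on days 1-3 a natural case to try.

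**Assumed.** Complete data, two-sided 5% tests, and two profiles for no catheter minus catheter: (a) +1.0 on days 1-14; (b) +2.0 on days 1-3 only. The 12 correlation structures are:
- random intercept SD 1.7 with slope SD 0.08 and residual SD 2.0
- compound symmetry 0.3, 0.4, 0.5, 0.6
- AR(1) 0.6, 0.7, 0.8, 0.9
- random-intercept share/AR of 0.3/0.5, 0.4/0.6, 0.5/0.5

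**Step 1: target values.** Mean difference over days 1-14: (a) 1.0; (b) 3 × 2.0 / 14 = 0.43.

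**Step 2: slope under linear time** (ordinary least squares, which is also the compound-symmetry answer). Slope = Σ(t − t̄)d(t) / Σ(t − t̄)².
- Baseline at day 0: t̄ = 7, Σ(t − 7)² = 280. (a) 7/280 = +0.025 per day. (b) 2 × (−6 − 5 − 4)/280 = −30/280 = −0.107 per day.
- Postoperative days only: t̄ = 7.5, Σ(t − 7.5)² = 227.5. (a) exactly 0. (b) 2 × (−6.5 − 5.5 − 4.5)/227.5 = −33/227.5 = −0.145 per day.

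**Step 3: power in one worked case** (profile a, compound symmetry 0.5, baseline at day 0; σ² = 2.64² = 6.97).
- Interaction: SE = √[2 × 6.97 × 0.5 / (60 × 280)] = 0.0204; z = 0.025/0.0204 = 1.23; power ≈ Φ(1.23 − 1.96) = 23%.
- Mean level: SE = √[2 × 6.97 × (0.5 + 0.5/14) / 60] = 0.353; z = 1.0/0.353 = 2.83; power ≈ Φ(2.83 − 1.96) = 81%.

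**Step 4: profile (a), linear time, generalized least squares, range over the 12 structures.**

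| Test | Power |
|---|---|
| Interaction, baseline at day 0 | 16-34% |
| Interaction, baseline at day -7 or -10, calendar lags | 29-66% |
| Joint 2-df test of the curves, baseline at day 0 | 59-95% |
| Mean level, days 1-14 | about 73-99% |

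**Step 5: profile (b), linear time.** The mean difference is +0.43. The slope is −0.012 to −0.107 per day with baseline at day 0. With baseline at day -7 or -10 and calendar lags it is −0.008 to −0.064, negative in all 12 structures. Positive values (the range becomes −0.064 to +0.132) arise only if baseline is coded day -7 or -10 in the mean model while correlation lags follow measurement order.

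**Step 6: categorical time.** With baseline as reference, the interaction terms are the daily level differences. The 14-df test has 98-100% power for profile (b), and 26-88% for profile (a) with baseline at day 0. The reported change still depends on the start point: (a) 1.0 from baseline to day 14 but 0 from day 1 to day 14; (b) 0 and −2.0. Neither choice returns both target values, 1.0 and 0.43.

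**The case against.** Five points count against a strong reading.

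- A reader might infer that level goes untested. It does not: the likelihood-ratio test of the curves covers it, with respectable power in Step 4. What stands is that this test is not the designated one and has no estimate attached.
- A reader might infer that the interaction is a weak test. That depends on the effect and the coding. For an early effect, which the infusion time makes plausible, the categorical interaction has 98-100% power and the mean difference only about 20-44%. Interest in trajectory is defensible; the difficulty is that the objective asks something else.
- Baseline is among the responses and the arms are randomized, so change from baseline to a given day equals, in expectation, the level difference on that day. This is right for one day. It does not supply the average over 14 days, and the start of the period is unstated.
- A reader might infer that the sign of the slope is at the mercy of the error structure. Step 5 does not support that: the sign turns only under one inconsistent pairing of time code and lags.
- A reader might take the descriptions of baseline timing as contradictory. The 7-10 days in Section 1.3, the approximate week in Section 6.3 and the window in Section 6.9 concern one call and are broadly compatible. What is missing is only the place of baseline on the time axis.

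**Conclusion.** The mismatch is plain in the text and needs no assumption. Objective 1, the outcome list and the opening of Aim 1 ask for a level, while the designated test and the only Aim 1 interval concern change, and no contrast for the two-week mean difference is written down. Followed as written, the plan can return a quantity that is zero, smaller than, or opposite in sign to the one named in the objective.

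The sizes are illustrative. They rest on assumed effect profiles and correlations, one SD for all days, complete data and, for the slope results, linear time.

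The consequence is confined to how Aim 1 is reported and read. A reader might extend it to the trial's main conclusion, but the day-2 noninferiority analysis has its own coefficient, margin and interval in Section 8.2 and is unaffected. Section 4.2 also names oxycodone tablet count, not two-week pain, as the main secondary outcome. The point should be corrected before analysis, but it does not threaten the trial.

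**What to change.** In Section 8.2, Secondary Aim 1, add as the Aim 1 estimate the between-arm difference in mean daily pain score over postoperative days 1-14 with its 95% confidence interval. Take it from the same mixed model with day as a category, arm, arm-by-day, and baseline score as a covariate rather than as one of the repeated responses. Report the arm-by-day test, the likelihood-ratio test (with its degrees of freedom) and the day-specific differences beside it. They are needed because the mean has only about 20-44% power for a 2-point effect confined to days 1-3.

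Alternatively, if trajectory is what the investigators want, reword Objective 1 (synopsis and Section 2.2) and the outcome in Section 1.3 to rate of change. Then state the form of time, the start of the follow-up period and the time code of the baseline score.

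Either route costs wording only. The data and the model family stay the same.
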